7.3 Adverse Events and Other Safety Aspects

The definitions of an AE or SAE can be found in [Appendix 12.4 Adverse Events: Definitions and Procedures for Recording, Evaluating, Follow-up and Reporting].

The investigator and medically qualified designee(s) are responsible for detecting, documenting and recording events that met the definition of an AE or SAE.

7.3.1 Time Period for Collecting Adverse Event and Serious Adverse Event Information

In order to identify any events that may be associated with study procedures and could lead to a change in the conduct of the study, Astellas collects AEs even if the subject has not received IP. AE collection begins after the signing of the ICF and will be collected until the ESV or when the subject is determined to be a screen failure.

7.3.2 Method of Detecting Adverse Events and Serious Adverse Events

The methods of recording, evaluating and assessing seriousness, causality and severity of AEs and SAEs are described in [Appendix 12.4 Adverse Events: Definitions and Procedures for Recording, Evaluating, Follow-up and Reporting]. Care will be taken not to introduce bias when detecting AEs and/or SAEs. Open-ended and nonleading verbal questioning of the subject is the preferred method to inquire about AE occurrences.

An AE with a change in severity is recorded as a new AE.

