7.2.4 Physical Examination

Physical examination will be performed as indicated in the Schedule of Assessments [Table 1] and whenever there is a medical indication.

The investigator should perform physical examinations in accordance with routine procedures. Any abnormal finding observed at screening must be assessed and documented as not clinically significant if a subject is to be enrolled in the study. After IP administration, new clinically significant findings or a worsening of an ongoing clinically significant abnormal condition will be recorded as an AE (see [Section 7.3 Adverse Events and Other Safety Aspects]).

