9.5 Analysis of Safety

9.5.1 Adverse Events

AEs will be coded using MedDRA. An AE with onset at any time from first dosing until last scheduled procedure will be classified as a TEAE for inclusion in the summary tabulations. An IP-related TEAE is defined as any TEAE with a causal relationship assessed as “yes” by the investigator, or records where the relationship is missing.

An overview and separate summaries of the number and percentage of subjects with TEAEs, drug-related TEAEs, TEAEs leading to withdrawal of dosing, IP-related TEAEs leading to withdrawal of dosing and TEAEs excluding SAEs that equal or exceed a threshold of 5% in any dose group under fed and fasted conditions will be presented by SOC, preferred term, by fed and fasted conditions for each dose group. Also included in the overview are the number and percentage of subjects with serious TEAEs, IP-related serious TEAEs, TEAEs leading to death and IP-related TEAEs leading to death.

AE data will be listed.

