12.4.1 Definition of Adverse Events

An AE is any untoward medical occurrence in a subject administered an IP, and which does not necessarily have to have a causal relationship with this IP. An AE can therefore be any unfavorable and unintended sign (including an abnormal laboratory finding), symptom, or disease (new or exacerbated) temporally associated with the use of IP whether or not considered related to the IP.

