12.4.4 Criteria for Defining the Severity of an Adverse Event

The investigator will use the following definitions to rate the severity of each AE:

- Mild (Grade 1): No disruption of normal daily activities
- Moderate (Grade 2): Affect normal daily activities
- Severe (Grade 3): Inability to perform daily activities

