## **6.4 Analysis of Safety**

### **6.4.1 Adverse Events**

AEs will be coded using MedDRA. An AE with onset at any time from first dosing until last scheduled procedure will be classified as a TEAE for inclusion in the summary tabulations. An IP-related TEAE is defined as any TEAE with a causal relationship assessed as “yes” by the investigator, or records where the relationship is missing.

An overview and separate summaries of the number and percentage of subjects with TEAEs, drug-related TEAEs, TEAEs leading to withdrawal of dosing, IP-related TEAEs leading to withdrawal of dosing and TEAEs excluding SAEs that equal or exceed a threshold of 5% in any dose group under fed and fasted conditions will be presented by SOC, preferred term, by fed and fasted conditions for each dose group. Also included in the overview are the number and percentage of subjects with serious TEAEs, IP-related serious TEAEs, TEAEs leading to death and IP-related TEAEs leading to death.

AE data will be listed.

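### Any change in AE severity, improvement included, opens a new AE while TEAEs are defined by onset alone, so a severity change in an event open at dosing can be misclassified

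*Protocol*

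**What the plan says.** - **Recording rule.** Protocol 7.3.2: "An AE with a change in severity is recorded as a new AE". The sentence stands alone and gives no direction of change.
- **TEAE rule.** Protocol 9.5.1: "An AE with onset at any time from first dosing until last scheduled procedure will be classified as a TEAE for inclusion in the summary" tables. SAP 6.4.1 repeats the rule: "An AE with onset at any time from first dosing until last scheduled procedure will be classified as a TEAE". Neither compares the event with its severity before dosing.
- **Collection window.** Protocol 7.3.1: "AE collection begins after the signing of the ICF and will be collected until the ESV". Screening can last up to 21 days (Protocol 4.1), so AEs that began before the first dose will be in the database.
- **Severity scale.** Protocol 12.4.4 introduces three grades, mild, moderate and severe, with "The investigator will use the following definitions to rate the severity of each AE".
- **Where worsening is mentioned.** The general AE definition in Protocol 12.4.1 covers a "symptom, or disease (new or exacerbated) temporally associated with the use of IP whether or not considered related to the IP". Protocol 7.2.4, on physical examination only, says that "new clinically significant findings or a worsening of an ongoing clinically significant abnormal condition will be recorded as an AE". Protocol 12.4.1.1 mentions worsening from baseline for abnormal tests. None of these refers to the rule in 7.3.2 or to the TEAE definition.
- **Not stated.** Neither document gives the onset date of a severity-change record, links it to its parent event, or says how a TEAE is assigned to a fed or fasted period. SAP 6.7 deals only with missing dates.

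**The concern.** A TEAE table should show events that appeared or got worse after dosing. An onset-only definition can do that if new records arise only from new or worsening events. Here the recording rule also opens a record when an event improves, and nothing in the TEAE rule filters it out. A moderate headache present on day -1 that becomes mild a few hours after the dose would produce a mild AE with postdose onset. It would be tabulated as treatment-emergent although the subject got better.

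AE frequency and severity form the first-listed secondary endpoint and are tabulated by fed and fasted condition within each dose group of 12. With counts that small, a single misclassified subject is visible in the table.

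**Working it through.** **Inputs.** Three severity grades (Protocol 12.4.4); 12 subjects per dose group (Protocol 9.1, SAP 3); the recording and TEAE rules given above. The plan states no figure of its own on this point that could be reproduced.

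**Step 1: list the possible changes.** For an event open at first dosing, the ordered pairs of different grades number 3 × 2 = 6: three increases (mild to moderate, mild to severe, moderate to severe) and three decreases (moderate to mild, severe to mild, severe to moderate). Mild is the lowest grade, so a mild event can only worsen or resolve. Resolution is not a change of grade on this scale and opens no record.

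**Step 2: apply the rules under each possible onset date.**

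| Onset date of the new record | Increases counted as TEAE | Decreases counted as TEAE | Misclassified |
|---|---|---|---|
| Date of the change (natural reading) | 3 of 3 | 3 of 3 | 3 decreases wrongly counted |
| Original onset date | 0 of 3 | 0 of 3 | 3 increases wrongly missed |
| TEAE requires an increase over predose severity | 3 of 3 | 0 of 3 | none |

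These are kinds of change, not expected frequencies. The table shows that settling the onset date alone does not repair the definition: one choice counts improvements and the other loses worsenings.

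**Step 3: size of one error.** One subject wrongly counted, or wrongly missed, in one dose group under one food condition is 1/12 = 8.3 percentage points. With one subject absent from that condition it is 1/11 = 9.1 points. The tables count subjects, so the shift appears only if the subject has no other TEAE of that term in that condition. How many such events will occur cannot be derived from the documents.

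**The case against.** The strongest reply is that the decisive step is inferred. No text says that the new record takes the date of the change. Protocol 12.2.3 refers to eCRF instructions that are not among the public documents and might settle it. Protocol 7.3 asks sites to record events that satisfy the AE definition, and 12.4.1 describes something unfavorable, new or exacerbated. A site could reasonably read 7.3.2 as meaning worsening only. This stands as a reason for caution: the misclassification may occur, not must occur. It does not remove the point. The sentence in 7.3.2 is not limited by those sections, and the rule that decides a table belongs in the SAP.

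The second reply is rarity. The subjects are healthy and screened for disease, recent infection and day -1 abnormalities. An improving record needs a moderate or severe event that is open at dosing and steps down rather than resolves. All AEs are listed, so a reader could find the parent record. This stands too, and it keeps the point small.

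A reader might infer more than the documents support:
- **One episode counted under both food conditions.** This needs an attribution rule that neither document states. It also needs a non-mild event that outlasts a washout of at least 10 days and then eases without resolving.
- **Passing the 5% threshold as a special defect.** With 12 subjects, every single TEAE, genuine or not, reaches 8.3%.
- **False drug-related events through missing causality.** Protocol 12.4.3 obliges the investigator to assess every AE, and treating missing as related applies to all TEAEs alike. The link to this rule is speculative.

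**Conclusion.** The wording gap is real and leads to a wrong classification under either onset date. On the natural reading, a moderate or severe event open at dosing that only eases afterwards is counted as a TEAE. On the other reading, a genuine postdose worsening of a predose event is not counted. The first result assumes that the severity-change record is dated at the change and that sites apply 7.3.2 literally.

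The effect is 8.3 percentage points per affected subject in one dose group and food condition. Few subjects are likely to be affected, and only the descriptive secondary AE tables are involved. The primary analysis of AUCinf, AUClast and Cmax does not use these data. Severity: minor. Confidence: medium, because of the unstated onset date.

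**What to change.** **Definition.** In Protocol 9.5.1 and SAP 6.4.1, define a TEAE as an AE that starts after IP administration, or that increases in severity after IP administration compared with its predose severity. For the fed and fasted tables, compare with the severity before that period's dose. This matches the within-period baseline that SAP 6.4.2 and 6.4.3 already use for laboratory and vital sign data.

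**Records.** Choose one route and write it down:
- **(a)** Change Protocol 7.3.2 so that only an increase in severity opens a new AE, with onset at the date of the increase.
- **(b)** Keep every severity step, link each record to the original event, and do not count records created by a decrease as TEAEs.

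**Cost.** Neither route needs additional assessments of subjects. Both need a sentence in the protocol and SAP and matching eCRF instructions. Route (a) shows fewer severity steps in the listing, so an easing before a dose would not be recorded as a step. Route (b) keeps that detail at the price of a linking field and a little more programming.

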7.3.3 Follow-up of Adverse Events

All AEs occurring during or after the subject has discontinued the study are to be followed up until resolved or judged to be no longer clinically significant, or until they become chronic to the extent that they can be fully characterized by the investigator.

If after the protocol-defined AE collection period (see [Section 7.3.1 Time Period for Collecting Adverse Event and Serious Adverse Event Information]), an AE progresses to an SAE, or the investigator learns of any (S)AE (serious adverse event or adverse event)

including death, where he/she considers there is reasonable possibility it is related to the IP or study participation, the investigator must promptly notify the sponsor.

7.3.4 Reporting of Serious Adverse Events

Prompt notification by the investigator to the sponsor of an SAE is essential, so that legal obligations and ethical responsibilities towards the safety of subjects and the safety of a study intervention under clinical investigation are met.

In the case of an SAE, the investigator must contact the sponsor by fax or email immediately (within 24 hours of awareness).

Procedures for reporting SAEs to the sponsor are described in [Section [12.4.5](#) Reporting Procedures for Serious Adverse Events].

7.3.5 Disease-related Events and/or Disease-related Outcomes Not Qualifying as Adverse Events or Serious Adverse Events

Not applicable.

7.3.6 Adverse Events of Special Interest

AEs of special interest are AEs that the sponsor may wish to carefully monitor. These AEs may be serious or nonserious and should be collected on the eCRF and the SAE worksheet and reported within 24 hours as described in [Section [12.4.5](#) Reporting Procedure for Serious Adverse Events]. These AEs are not considered SAEs unless they meet the definition of an SAE. AEs of special interest in this study will include:

- Increased heart rate and tachycardia
- Increased blood pressure
- Hypersensitivity reactions

7.3.7 Special Situations

Certain special situations observed in association with the IP, such as incorrect administration (e.g., wrong dose of IP or background therapy) are collected in the eCRF, as protocol deviations per [Section [10.3](#) Major Protocol Deviations] or may require special reporting, as described below. These special situations are not considered AEs, but are required to be communicated to Astellas as per the timelines defined below.

If a special situation is associated with, or results in, an AE, the AE is to be assessed separately from the special situation and captured as an AE in the eCRF. If the AE meets the definition of an SAE, the SAE is to be reported as described in [Section [12.4.5](#) Reporting Procedures for Serious Adverse Events] and the details of the associated special situation are to be included in the clinical description on the special situation worksheet.

The special situations are:

- Pregnancy
- Medication error, overdose and “off-label” use
- Misuse/abuse

- Occupational exposure
- Suspected drug-drug interaction

Instructions and procedures for reporting special situations are provided in [Appendix 12.4.6 Reporting Procedures for Special Situations].

7.3.8 Supply of New Information Affecting the Conduct of the Study

When new information becomes available that is necessary for conducting the study properly, the sponsor will inform all investigators involved in the study as well as the appropriate regulatory authorities. Investigators should inform the IRB/IEC of such information when needed.

The investigator will also inform the subjects, who will be required to sign an updated ICF in order to continue in the study.

7.3.9 Urgent Safety Measures

An urgent safety measure (USM) is an intervention that is not defined by the protocol and can be put in place with immediate effect without needing to gain prior approval by the sponsor, relevant competent authorities, IRB/IEC, where applicable, in order to protect subjects from any immediate hazard to their health and/or safety. Either the investigator or the sponsor can initiate a USM. The cause of a USM can be safety-, product- or procedure-related.

7.3.10 Reporting Urgent Safety Measures

In the event of a potential USM, the investigator must contact the study physician (within 24 hours of awareness). Full details of the potential USM are to be recorded in the subject's medical records. The sponsor may request additional information related to the event to support their evaluation.

If the event is confirmed to be a USM, the sponsor will take appropriate action to ensure the safety and welfare of the subjects. These actions may include but are not limited to a change in study procedures or study dosing, halting further enrollment in the study, or stopping the study in its entirety. The sponsor or sponsor's designee will notify the relevant competent authorities and concerned ethics committee within the timelines required per current local regulations, and will inform the investigators, as required. When required, investigators must notify their IRB/IEC within timelines set by regional regulations.

7.4 Pharmacokinetics

7.4.1 Analysis of Mirabegron in Plasma

Blood samples will be collected for pharmacokinetic analysis of mirabegron as indicated in the Schedule of Assessments [Table 1].

The actual date and time of pharmacokinetic blood sample collection will be captured in the source. Blood sample collection, handling and storage will be described in the laboratory manual. Plasma samples will be analyzed using a validated method.

7.5 Pharmacodynamics | Immunogenicity

Not applicable.

7.6 Electronic Clinical Outcome Assessment

Not applicable.

7.7 Other Assessments

Not applicable.

7.8 Total Amount of Blood

The approximate total blood volume taken per subject will be as follows:

Table 6 Blood Volume

Sample Type	Number of Samples	Sample Volume (mL)	Total Volume (mL)
Clinical Laboratory Tests	6	7.0 (12.0)†	47.0
Pregnancy Test (Female Subjects Only)	3	3.0	9.0
FSH Test (Postmenopausal Female Subjects Only)	1	3.0	3.0
Mirabegron Pharmacokinetics	34	4.0	136.0
Total			183.0 for males 192.0 for females 186.0 for postmenopausal females

FSH: follicle-stimulating hormone

† Includes serology test at screening.

Additional blood may be drawn for safety reasons. The maximum amount of blood drawn during the study will not exceed 400 mL.

8 DISCONTINUATION

8.1 Discontinuation of Individual Subject(s) From Study Dosing

A discontinuation from dosing is defined as a subject who enrolled in the study and for whom study dosing is permanently discontinued for any reason.

The subject is free to withdraw from the study dosing and/or study for any reason and at any time without giving reason for doing so and without penalty or prejudice. The investigator is also free to discontinue the subject from study dosing or to terminate a subject's involvement in the study at any time if the subject's clinical condition warrants it.

The reason for discontinuation from study dosing must be documented in the subject's medical records.

A subject must discontinue study dosing for any of the following reasons:

- Subject requests to stop dosing
- Any clinical AE, laboratory abnormality or intercurrent illness, in the opinion of the investigator, indicates continued dosing is not in the best interest of the subject
- Hepatic function parameters: ALT or AST > 3 × ULN and/or TBL > 2 × ULN; for additional information on hepatic parameter abnormalities, refer to [Appendix 12.5 Liver Safety Monitoring and Assessment]
- Cardiac repolarization dysfunction: QTcF > 500 msec and/or if QTcF change from baseline > 60 msec at repeat measurements

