All medicinal products other than the IP(s), including prescribed or nonprescribed drugs (including vitamins, natural and herbal remedies, e.g., St. John's Wort and traditional Chinese medicine), used from first IP administration until the ESV (including washout between periods) will be considered concomitant medication.

Subjects will only be allowed to use the following concomitant medication, if needed, from first IP administration until the ESV (including washout between periods):

- Paracetamol (up to 2 g/day)
- Topical dermatological products, including corticosteroid products
- Hormonal contraceptives
- HRT

If a subject's health condition necessitates the use of any medication other than the permitted medications during the study, the investigator and medical monitor, or designee(s), will discuss the case and determine if the subject should be withdrawn from the study and/or excluded from analysis sets, depending on if, and how, the medication(s) used influence(s) the study outcome. The nonpermitted concomitant medication will be recorded as a protocol deviation.

All concomitant treatment (medication and nonmedication therapy) will be documented.

Duration of Dosing:

Two single periods separated by a washout of at least 10 days between IP administrations in each period

Dosing Discontinuation Criteria:

A subject must discontinue study dosing for any of the following reasons:

- Subject requests to stop dosing
- Any clinical adverse event (AE), laboratory abnormality or intercurrent illness, in the opinion of the investigator, indicates continued dosing is not in the best interest of the subject
- Hepatic function parameters: ALT or AST $> 3 \times$ ULN and/or TBL $> 2 \times$ ULN
- Cardiac repolarization dysfunction: QTcF > 500 msec and/or if QTcF change from baseline > 60 msec at repeat measurements

Statistical Methods:

Sample Size Justification:

A total of 24 subjects (12 subjects per dose group) will be enrolled. Subjects who discontinue early from the study may be replaced at the discretion of the sponsor.

Based on data from Study 178-CL-091, a Chinese phase 1 study, the intrasubject coefficient of variation (CV) for pharmacokinetic parameters AUC_{inf} , AUC_{last} and C_{max} of the 50 mg mirabegron dose are estimated to be between 33% and 60%. Assuming the underlying variability is similar to 60% and an observed ratio between fasted and fed conditions of 100%, the 90% CI will lie within (60, 167) with $> 80\%$ probability.

Efficacy:

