12.5 Liver Safety Monitoring and Assessment

The purpose of this appendix is to provide guidance for the monitoring of drug-induced liver injury during the course of the study. It should be noted that this section does not specify the end-of-study analyses of liver enzymes. Any subject enrolled in a study with active drug therapy and reveals an increase of serum aminotransferases (ATs) to $> 3 \times \text{ULN}$ or $\text{TBL} > 2 \times \text{ULN}$ should undergo detailed testing for liver enzymes (including at least alkaline phosphatase [ALP], ALT, AST and TBL). Testing should be repeated within 72 hours of notification of the test results. Subjects should be asked if they have any symptoms suggestive of hepatobiliary dysfunction.

Definition of Liver Abnormalities

Confirmed abnormalities will be characterized as moderate and severe where ULN is as shown below.

Table 9 Moderate and Severe Liver Abnormalities

	ALT or AST		TBL
Moderate	$> 3 \times \text{ULN}$	or	$> 2 \times \text{ULN}$
Severe	$> 3 \times \text{ULN}$	and†	$> 2 \times \text{ULN}$

ALT: alanine aminotransferase; AST: aspartate aminotransferase; TBL: total bilirubin; ULN: upper limit of normal

†Samples taken simultaneously or within a maximum of 24 hours.

In addition, the subject should be considered to have severe hepatic abnormalities for any of the following:

- ALT or AST $> 8 \times \text{ULN}$
- ALT or AST $> 5 \times \text{ULN}$ for more than 2 weeks
- ALT or AST $> 3 \times \text{ULN}$ and† TBL $> 2 \times \text{ULN}$ or international normalized ratio (INR) > 1.5 (if INR testing is applicable/evaluated)
- ALT or AST $> 3 \times \text{ULN}$ with the appearance of fatigue, nausea, vomiting, right upper quadrant pain or tenderness, fever, rash and/or eosinophilia ($> 5\%$)

† Samples taken simultaneously or within a maximum of 24 hours.

The investigator may determine that abnormal liver function results, other than as described above, may qualify as moderate or severe abnormalities and require additional monitoring and follow-up.

Follow-up Procedures

Confirmed moderate and severe abnormalities in hepatic functions should be thoroughly characterized by obtaining appropriate expert consultations, detailed pertinent history, physical examination and clinical laboratory tests. The study site personnel are to complete the liver abnormality case report form (LA-CRF). Subjects with confirmed abnormal liver function testing should be followed as described below.

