Confirmed moderately abnormal liver function tests should be repeated 2 to 3 times weekly, and then weekly or less if abnormalities stabilize or the IP has been discontinued and the subject is asymptomatic.

Severe hepatic liver function abnormalities as defined above, in the absence of another etiology, may be considered an important medical event and may be reported as a SAE. The sponsor should be contacted and informed of all subjects for whom severe hepatic liver function abnormalities possibly attributable to IP are observed.

To further assess abnormal hepatic laboratory findings, the investigator is expected to:

- Obtain a more detailed history of symptoms and prior or concurrent diseases. Symptoms and new-onset diseases are to be recorded as “AEs” within the eCRF. Illnesses and conditions such as hypotensive events and decompensated cardiac disease that may lead to secondary liver abnormalities should be noted. Nonalcoholic steatohepatitis is seen in obese hyperlipoproteinemic and/or diabetic subjects and may be associated with fluctuating AT levels. The investigator should ensure that the medical history form captures any illness that predates study enrollment that may be relevant in assessing hepatic function.
- Obtain a history of concomitant drug use (including nonprescription medication, complementary and alternative medications), alcohol use, recreational drug use and special diets. Medications are to be entered in the eCRF. Information on alcohol, other substance use and diet should be entered on the LA-CRF or an appropriate document.
- Obtain a history of exposure to environmental chemical agents.
- Based on the subject’s history, other testing may be appropriate including:
 - Acute viral hepatitis (A, B, C, D, E or other infectious agents)
 - Ultrasound or other imaging to assess biliary tract disease
 - Other clinical laboratory tests, including INR and direct bilirubin
- Consider gastroenterology or hepatology consultations
- Submit results for any additional testing and possible etiology on the LA-CRF or an appropriate document

Study Dosing Discontinuation

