In the absence of an explanation for increased liver function tests, such as viral hepatitis, preexisting or acute liver disease, or exposure to other agents associated with liver injury, the subject may be discontinued from study dosing. The investigator may determine that it is not in the subject’s best interest to continue study dosing. Discontinuation of study dosing should be considered if:

- ALT or AST $> 8 \times$ ULN
- ALT or AST $> 5 \times$ ULN for more than 2 weeks
- ALT or AST $> 3 \times$ ULN and† TBL $> 2 \times$ ULN or INR > 1.5 (if INR testing is applicable/evaluated)
- ALT or AST $> 3 \times$ ULN with the appearance of fatigue, nausea, vomiting, right upper quadrant pain or tenderness, fever, rash and/or eosinophilia ($> 5\%$)

† Samples taken simultaneously or within a maximum of 24 hours.

In addition, if close monitoring for a subject with moderate or severe hepatic laboratory tests is not possible, study dosing should be discontinued.

Hy's Law definition: Drug-induced jaundice caused by hepatocellular injury, without a significant obstructive component, has a high rate of bad outcomes, from 10% to 50% mortality (or transplant).

The 2 "requirements" for Hy's Law are:

1. Evidence that a drug can cause hepatocellular-type injury, generally shown by an increase in AT elevations $> 3 \times \text{ULN}$ ("2 $\times \text{ULN}$ elevations are too common in treated and untreated subjects to be discriminating")
2. Cases of increased TBL (at least $2 \times \text{ULN}$) with concurrent AT elevations at least $3 \times \text{ULN}$ and no evidence of intra- or extra-hepatic bilirubin obstruction (elevated ALP) or Gilbert's syndrome [Temple, 2006]

FDA Guidance for Industry titled, "Drug-induced Liver Injury: Premarketing Clinical Evaluation" issued by the FDA on July 2009:

1. The drug causes hepatocellular injury, generally shown by a higher incidence of 3-fold or greater elevations above the ULN of ALT or AST than the (nonhepatotoxic) control drug or placebo
2. Among subjects showing such AT elevations, often with ATs much greater than $3 \times \text{ULN}$, 1 or more also show elevation of serum TBL to $> 2 \times \text{ULN}$, without initial findings of cholestasis (elevated serum ALP)
3. No other reason can be found to explain the combination of increased AT and TBL, such as viral hepatitis A, B, or C; pre-existing or acute liver disease; or another drug capable of causing the observed injury

References

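### Liver stopping is mandatory in Section 8.1 and the synopsis but discretionary in Appendix 12.5, and SAE reporting of potential Hy's Law cases is likewise both required and optional

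*Protocol*

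**What the plan says.** **Dosing, main text.** The synopsis introduces its dosing discontinuation criteria with "A subject must discontinue study dosing for any of the following reasons", and Section 8.1 uses the same lead-in. The hepatic item in both is "Hepatic function parameters: ALT or AST > 3 × ULN and/or TBL > 2 × ULN". Either abnormality alone is enough, and no allowance is made for an alternative cause or a repeat test. The QTcF item beside it does mention repeat measurements. Section 8.1 then points to Appendix 12.5 for further information on abnormal hepatic results.

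**Dosing, Appendix 12.5.** Under its own subheading on dosing discontinuation, the appendix begins "In the absence of an explanation for increased liver function tests" and continues that "the subject may be discontinued from study dosing". It then says "Discontinuation of study dosing should be considered if" and lists four situations:

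- ALT or AST > 8 × ULN
- ALT or AST > 5 × ULN for more than 2 weeks
- ALT or AST > 3 × ULN together with TBL > 2 × ULN or INR > 1.5
- ALT or AST > 3 × ULN with listed symptoms or eosinophilia > 5%

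Its firmest stopping instruction is conditional: "if close monitoring for a subject with moderate or severe hepatic laboratory tests is not possible, study dosing should be discontinued".

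**Reporting.** Section 12.4.1.2 says that aminotransferase and bilirubin elevations meeting the Appendix 12.5 criteria, without another cause, are always important medical events and go through the SAE procedure in 12.4.5. The follow-up text of Appendix 12.5 says that severe abnormalities without another etiology *may* be treated that way.

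**The concern.** A stopping rule should give one answer for one laboratory result. Here the main text and the liver appendix give two, and neither says which prevails. Both strict sections also send the reader to the looser one: Section 8.1 for more information, and Section 12.4.1.2 for detailed instructions. Staff handling an abnormal liver result would naturally work from the liver appendix.

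Three things depend on the reading:

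- **Safety.** A healthy volunteer, who by Section 2.3 gains no benefit from mirabegron, could receive a second dose that Section 8.1 forbids.
- **Deviations and analysis.** Section 10.3 makes it a major deviation (PD2) to keep a subject who has met withdrawal criteria. Under Section 9.2.2, major deviations put inclusion in the pharmacokinetic analysis set under case-by-case review, in a study with 12 subjects per dose group.
- **Expedited reporting.** A site that follows Appendix 12.5 would inform the sponsor of a severe case possibly attributable to the drug. It could still omit the SAE worksheet and miss the 24-hour limit in Section 12.4.5.

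**Working it through.** The plan states no figure on this point to reproduce. The check compares the texts at specific results and then looks at timing.

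**1. Same result, two decisions.** Table 9 in Appendix 12.5 defines a moderate abnormality as ALT or AST > 3 × ULN, or TBL > 2 × ULN. It defines a severe one as both together. The moderate definition matches the mandatory trigger in Section 8.1. I read the INR alternative in the third criterion as tied to ALT or AST > 3 × ULN.

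| Result | Section 8.1 and synopsis | Appendix 12.5 |
|---|---|---|
| ALT 4 × ULN, normal TBL and INR, no symptoms or eosinophilia | Must stop | Moderate; none of the four listed criteria met; stopping optional if unexplained |
| TBL 2.5 × ULN alone | Must stop | Moderate; none of the four listed criteria met; stopping optional if unexplained |
| ALT 4 × ULN with TBL 2.5 × ULN, no other cause | Must stop | Severe; stopping to be considered |
| ALT > 8 × ULN | Must stop | Severe; stopping to be considered |

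In the first two rows the thresholds differ. In the last two only the force of the instruction differs.

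**2. Does Appendix 12.5 really contemplate continued dosing?** Two sentences suggest that it does. Retesting of moderate abnormalities can drop to "weekly or less if abnormalities stabilize or the IP has been discontinued and the subject is asymptomatic", which treats stopping as one possibility among others. The instruction that "if close monitoring for a subject with moderate or severe hepatic laboratory tests is not possible, study dosing should be discontinued" covers moderate cases too. It would have no purpose if Section 8.1 had already stopped every such subject.

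**3. When the difference can matter.** Each subject receives one dose per period, so only the period 2 dose can be withheld. Table 1 schedules clinical laboratory tests at screening, on day -1 and day 5 of each period, and at the end-of-study visit:

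1 + 2 + 2 + 1 = 6 samples

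This agrees with Table 6, including its volume: 12.0 + 5 × 7.0 = 47.0 mL. Two of these panels fall between the doses: day 5 of period 1 and day -1 of period 2.

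**4. Can the 2-week criterion be met before period 2?** Assume there is no day 0. Eligibility excludes liver tests above 1.5 × ULN on day -1 of period 1. The doses are at least 10 days apart, so the earliest period 2 dose falls on day 11.

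- Day -1 to day 1, plus day 1 to day 11: 1 + 10 = 11 days, less than 14.
- Day 5 to day 11: 6 days, less than 14.

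At the minimum interval an elevation cannot have lasted more than 2 weeks, so the whole isolated, asymptomatic band from 3 to 8 × ULN is affected. With an interval of 14 days or more, the criterion becomes reachable in principle.

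**5. Retest window on day -1 of period 2.** Appendix 12.5 says "Testing should be repeated within 72 hours of notification of the test results". With same-day notification the dose is due about 24 hours later, so the window can close about 72 − 24 = 48 hours after the dose was due. A site working from Appendix 12.5 alone could dose before the value is confirmed.

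**6. Reporting overlap.** The severe class contains ALT or AST > 3 × ULN with TBL > 2 × ULN. For that combination without another cause, Section 12.4.1.2 says *always* and Appendix 12.5 says *may*. The conflict does not extend to the rest of the severe class.

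**The case against.** The best defense is that a permissive sentence does not cancel a mandatory one. A site that stops dosing and retests complies with both texts. Section 8.1 cites Appendix 12.5 only for additional information, the appendix describes itself as monitoring guidance, and PD2 makes failure to withdraw a major deviation. Appendix 12.5 also lets the investigator stop for any unexplained increase, so a subject with ALT 4 × ULN can be stopped under either text. The 72 hours are an outer limit for retesting and do not authorize dosing in the meantime. On reporting, the specific Hy's Law rule can be read as governing its own subset, and the sponsor can itself classify an event as serious under Section 12.4.2.

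Much of this stands. A compliant reading exists, nothing in Appendix 12.5 orders a dose to be given, and harm requires a site to rely on the appendix alone. The 11-day calculation holds only at the minimum interval. But the defense requires the reader to infer a precedence that the protocol does not state. It also leaves the close-monitoring sentence unexplained, since that sentence makes sense only if dosing can otherwise continue at the Section 8.1 trigger. Being allowed to stop is not the same as being required to. For a potential Hy's Law case, *always* and *may* cannot both be the operating instruction.

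**Conclusion.** The concern holds. The two texts give different dosing decisions for:

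- ALT or AST from above 3 up to 8 × ULN, when isolated and asymptomatic (no TBL > 2 × ULN, INR > 1.5 or eosinophilia > 5%, and not > 5 × ULN for more than 2 weeks)
- TBL > 2 × ULN alone

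They also conflict on SAE reporting of potential Hy's Law cases.

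The practical weight is modest. At most one dose per subject is at stake, the documents give no event rate so no frequency is claimed, and the sample size and primary model do not change. It should still be fixed, because it concerns stopping and expedited-reporting instructions in healthy volunteers. The threshold comparison rests on the protocol text and the INR reading given above. The timing points assume no day 0, same-day notification and, for the 2-week criterion, an interval between doses shorter than 14 days.

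**What to change.** Let the mandatory rule in Section 8.1 and the synopsis govern dosing. In Appendix 12.5, replace the discontinuation criteria and the close-monitoring sentence with:

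> Study dosing must be discontinued at ALT or AST > 3 × ULN and/or TBL > 2 × ULN, as stated in Section 8.1, whether or not another explanation is found.

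Keep the 72-hour retest and the follow-up steps.

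In the follow-up text of Appendix 12.5, state that ALT or AST > 3 × ULN with TBL > 2 × ULN, in the absence of other causes, must be reported as an SAE within 24 hours under Section 12.4.5. Leave *may* for the other severe abnormalities.

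The cost is an amendment confined to Appendix 12.5, handled under Section 12.1.3. No assessment, sample or analysis changes. A subject who could have continued under the present appendix loses the period 2 dose, as Section 8.1 already requires.
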